There are large disparities in the access to and effectiveness of many available preventive strategies for Severe-Early Childhood Caries (S-ECC) and Early Childhood Caries (ECC), two of the disease presentations for dental caries in children, one of the most common chronic diseases of childhood. This inequity frequently results in progression of dental disease in higher risk groups to an advanced stage, during which cavitated carious lesions and/or pulpal infections develop. When primary prevention fails or is not accessible, effective treatments that are safe, simple, low-cost, and acceptable to patients are necessary to decrease disease morbidity.

The product, 38% percent Silver Diamine Fluoride (SDF; also known as Diammine Silver Fluoride- DSF) is a potentially safe, non-invasive, quick, simple to use agent that will be tested in this trial for its ability to arrest cavitated lesions with exposed dentin in primary teeth (Chu et al., 2002; Llodra et al., 2005; Tan et al., 2010; Liu et al., 2012). SDF has been used since the 1970s in Asia as a caries arresting and anti-hypersensitivity agent, and in 2014 SDF was cleared by the Food and Drug Administration (FDA) as a medical device to manage hypersensitive teeth in adults.

This trial is a Phase III, multisite, randomized, placebo-controlled superiority trial, with two parallel groups: SDF/placebo, applied at baseline and at approximately 6 months. The primary hypothesis of the trial is that 38% SDF is superior to placebo for arresting cavitated caries lesions with dentin exposed in primary teeth when assessed approximately 6 months after initial application.

Objectives:**Primary:**

- Aim 1: Assess the efficacy of 38% SDF applied once, to arrest cavitated lesions exposing dentin clinically, in the primary dentition at 6 month follow-up.

Secondary:

[figure not shown]
- Aim 2: Assess the efficacy of 38% SDF applied twice, approximately 6 months apart, to arrest cavitated lesions exposing dentin clinically, in the primary dentition at 8 month follow-up.
- Sub Aim 2a: Compare the effect of one application of 38% SDF at 3 and 6 month follow-ups.
- Aim 3: Assess the impact of 38% SDF applied twice, approximately 6 months apart, on pain in children.
- Sub Aim 3a: Assess the impact of 38% SDF on pain after a single application (assessed at 3 and 6 months).

Tertiary:

- Aim 4: Assess the impact of 38% SDF on Family-Level Outcomes:

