12.1 Trial Hypotheses

The Primary Hypothesis:

- 38% Silver Diamine Fluoride (SDF) will arrest cavitated caries lesions (ICDAS 5 or 6) in primary teeth, measured by a change in dentin hardness, without a change in ICDAS severity score, after a single application (measured at approximately 6 months post initial application). This occurs as a result of the halting of the caries disease process, which occurs very soon after application of SDF due to its strong antimicrobial and remineralizing properties.

The Secondary Hypotheses:

- 38% Silver Diamine Fluoride (SDF) will arrest a greater proportion of cavitated caries lesions (ICDAS 5 or 6) in primary teeth after two applications, approximately 6 months apart (measured at approximately 8 months after initial SDF application).
- Lesions arrested approximately 3 months after a single application will remain stable when re-assessed at approximately 6 months.
- 38% Silver Diamine Fluoride (SDF) will decrease the proportion of children in pain, number of pain episodes associated with treated teeth for children, and pain score associated with treated teeth. The hypothesis is that SDF will do this as it is an anti-hypersensitivity agent, extremely efficient at blocking dentinal tubules, and also because it can arrest cavitated lesions, and thus decrease pain.

The Tertiary Hypotheses:

- 38% Silver Diamine Fluoride (SDF) will increase Oral Health-Related Quality of Life (OHRQoL) as a result of decreasing pain and arresting caries lesions.
- 38% Silver Diamine Fluoride (SDF) will be an acceptable treatment by parents/guardians of young children.

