Note: As this trial may enroll siblings, at the time of analyses we intend to explore the correlations within participants and correlations between siblings to aid in determining the appropriate modeling technique to use. As described above the current analysis plan uses GEE models to account for correlations among multiple cavities within a participant. The GEEs could be extended to account for siblings by correlating all cavities within a family, rather than within a participant. However, this assumes the same within family correlation. An alternative approach is to account for the two levels of correlations (cavities within participants, participants within families) by switching the analyses to use generalized linear mixed models (GLMM) instead of GEE. One difficulty we anticipate with a switch to GLMM is estimation of the random effects – the number of families with enrolled siblings may not be large enough to properly estimate the two random effects within the GLMMs.

Aim 2 (Cavitated caries lesion arrest at 8 months follow-up): The same GEE model for binary outcomes as used for Aim 1 will be used to compare the proportion of arrested lesions at approximately 8-months to examine Aim 2.

Sub-Aim 2a (Compare the effect of one application of 38% SDF at 3 and 6 months follow-up on caries lesion arrest): A longitudinal (repeated measures) model for binary data that incorporates both the correlation within each subject at each time and across the time points will be used to compare the proportion of arrested caries lesions at approximately 3 and 6 months. Trial site will be included as a covariate.

Aim 3 and Sub-Aim 3a (pain): At the 3-, 6-, and 8-month visits, the proportion of participants who have experienced pain with treated teeth during the follow-up period will be compared between the SDF and placebo-treated groups using Cochran-Mantel-Haenszel chi-square tests, with trial sites as the strata.

The total number of episodes of pain associated with trial teeth per participant (calculated by adding all reports of pain throughout the trial verified by a clinical exam to be associated with a trial tooth) during the follow-up period will be compared between the SDF and placebo treated groups using generalized linear models (GLMs) for count data, with trial site included as a covariate. The DDQ score will be compared between groups using analysis of covariance at each follow-up visit, with trial site included as a covariate.

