6.1. Statistical Comparisons

All statistical comparisons will be made using a two-sided test. The interim and final analyses will be conducted using p-value thresholds of 0.000001709 and 0.00099938, respectively, for the primary analysis. The overall type I error for interim and final primary endpoint analysis is two-sided $\alpha=0.1\%$.

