6.11.4. Secondary Efficacy Hypotheses, Endpoints, and Analyses

The gatekeeping procedure will assess the hypotheses associated with the two key secondary endpoints in the following prescribed hierarchy. Each endpoint will be assessed using a two-sided $\alpha=0.1\%$ significance level, however the second endpoint in the hierarchy below will be gated by the first endpoint meeting significance. Otherwise, no inference will be drawn on the second endpoint in the hierarchy below, however results with p-values will still be calculated and presented in the table outputs.

1. Secondary Endpoint #1: Cavitated Caries Lesion Arrest at 8 months (Aim 2)

This secondary endpoint will be tested first. The same GEE model for binary outcomes as used for Aim 1 will be used to compare the proportion of arrested lesions at 8-months to examine Aim 2.

2. Secondary Endpoint #2: Pain (Aim 3)

This secondary endpoint will be tested second only if the first secondary endpoint reaches statistical significance.

Aim 3: At the 8-month visits, the proportion of treated lesions that have experienced pain during the follow-up period before or at the visit will be compared between the SDF and placebo-treated groups using GEE models with a logit link for the lesion-specific binary outcomes yes/no lesion pain at each visit, using an exchangeable correlation to account for non- independence among multiple treated lesions within a participant. The GEE models will include study site as a covariate due to stratified randomization by site.

Other Sub-Aim Secondary Endpoint Analyses:

For Sub-Aim 2a (Cavitated caries lesion arrest at 3 months), the same GEE model for binary outcomes as used for Aim 1 will be used to compare the proportion of arrested lesions at 3 months to examine Aim 2a. Sub-Aim 2a is not included in the hierarchical testing strategy.

For Sub-Aim 2b (Stability of the effect of one application of 38% SDF on caries lesion arrest between 3 and 6 months), a longitudinal (repeated measures) model for binary data that incorporates both the correlation within each subject at each time and across the time points will be used to compare the proportion of arrested caries lesions at 3 and 6 months. Study site will be included as a covariate due to stratified randomization by site.

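### The hypothesis that lesions arrested at 3 months stay arrested at 6 months is matched only to a comparison of overall arrest proportions, which bounds lesion-level retention but does not estimate it

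*SAP*

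**What the plan says.** The hypothesis is in Protocol 12.1, among the secondary hypotheses: "Lesions arrested approximately 3 months after a single application will remain stable when re-assessed at approximately 6 months". Its subject is a set of lesions identified at 3 months and followed to 6 months.

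The analysis is given in two places. Protocol 12.4 (there called Sub-Aim 2a) plans a longitudinal binary model that "will be used to compare the proportion of arrested caries lesions at approximately 3 and 6 months". SAP 6.11.4 repeats this as Sub-Aim 2b, labelled "Stability of the effect of one application of 38% SDF on caries lesion arrest between 3 and 6 months". The SAP model "incorporates both the correlation within each subject at each time and across the time points", includes site as a covariate, and "will be used to compare the proportion of arrested caries lesions at 3 and 6 months".

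The objective in the Protocol Summary is broader: "Compare the effect of one application of 38% SDF at 3 and 6 month follow-ups". On testing, SAP 6.1 says "All statistical comparisons will be made using a two-sided test".

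Neither document restricts an analysis to lesions arrested at 3 months, tabulates lesion status at 3 months against 6 months, estimates relapse or retention, or sets a margin for stability.

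**The concern.** The hypothesis concerns a conditional probability: the chance that a lesion is arrested at 6 months given that it was arrested at 3 months. The planned model compares two overall proportions. If some arrested lesions soften while an equal number of others harden, the overall proportion does not move. Conversely, if every arrested lesion holds and further lesions arrest, the proportion rises although nothing relapsed.

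Modelling correlation across visits gives a correct standard error for the difference. It does not change the quantity compared. A two-sided test without a margin adds a second limitation: failing to find a difference is not evidence that there is none.

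At stake is the only stated hypothesis on how durable a single application is between 3 and 6 months. Followed as written, the plan describes the net change in arrest but leaves that hypothesis without an estimate.

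**Working it through.** **Inputs.** From the documents: 55% arrest with SDF and 45% with placebo, 3 lesions per child, within-child correlation 0.5, 1144 children (Protocol 12.2, SAP section 4); 1:1 allocation (SAP section 5); about 79% arrest after one application in the cited literature (Protocol 2.2). The rate of new arrest between 3 and 6 months is not given, so it is treated as an assumption over a range.

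**The plan's own figure.** Sub-Aim 2b has no sample size, power or margin to reproduce. The only related figure is 1144, for the primary endpoint. At two-sided alpha 0.001 and 80% power, 55% against 45% needs 852 lesions per arm (pooled variance). With design effect 1 + (3 − 1) × 0.5 = 2, that is 852 × 2 / 3 = 568 children per arm, 1136 in total before the interim-look adjustment. With the stated efficacy and futility thresholds, power at 1144 is 80.1%. No stated figure is in dispute, and these inputs are reused below.

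**Step 1: what equal proportions imply.** Let m be the proportion arrested at both visits. The smallest possible retention is max(0, 2m − 1) / m; the largest is 100%.

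- m = 0.55: 0.10 / 0.55 = 18%, so 18% to 100%.
- m = 0.79: 0.58 / 0.79 = 73%, so 73% to 100%.
- m = 0.45 (placebo assumption): 2m − 1 is negative, so 0% to 100%.

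**Step 2: how much relapse is hidden.** The proportions stay equal when m × relapse = (1 − m) × new arrest, so hidden relapse = (1 − m) × new arrest / m.

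| New arrest among the rest (assumed) | Hidden relapse, m = 0.55 | Hidden relapse, m = 0.79 |
|---|---|---|
| 5% | 0.45 × 0.05 / 0.55 = 4% | 0.21 × 0.05 / 0.79 = 1.3% |
| 10% | 0.45 × 0.10 / 0.55 = 8% | 0.21 × 0.10 / 0.79 = 2.7% |
| 30% | 0.45 × 0.30 / 0.55 = 25% | 0.21 × 0.30 / 0.79 = 8% |

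**Step 3: in lesions.** Half of 1144 is 572 SDF children; 572 × 3 = 1716 lesions, and 55% of these is about 944 arrested at 3 months. Retention of 100%, 90% and 70% then means 0, 94 and 283 relapses. With as many new arrests, the difference between visits is zero each time.

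**Step 4: does modelling the correlation help?** A GEE time contrast was simulated with 572 children, 3 lesions each, correlation 0.5 at 3 months and 55% arrested at both visits, with 60 runs per scenario. At true retention of 99%, 90%, 70% and 55%, the mean time effect on the log-odds scale lay between −0.009 and 0.000. Rejection at 0.05 was 3% to 8%. With 60 runs the Monte Carlo standard error around 5% is √(0.05 × 0.95 / 60) = 2.8 points, so these rates do not separate the scenarios.

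**Step 5: would a direct estimate be useful?** If retention were 90% (assumed) among 944 lesions with no dropout, the 95% half-width is 1.96 × √(0.9 × 0.1 / 944) = 1.9 points. With design effect 2 it is 1.9 × √2 = 2.7 points.

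**The case against.** The planned model does answer the aim as it is usually worded. The Protocol Summary, Protocol 3.1 and 3.2.2, and SAP 3 and 3.2 all ask for a comparison of the effect of one application at 3 and 6 months, and the SAP label speaks of stability of the effect. The lesion-level wording occurs once, in Protocol 12.1. This stands: the model is not a mistake and should be kept. The mismatch is with that one hypothesis.

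A reader might infer that the plan will declare lesions stable whenever the difference is non-significant. No such rule is written; the documents say only that the proportions will be compared. If arrest rose because further lesions hardened, the direction would also be visible in the estimate.

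Large offsets may be unlikely in the SDF arm. Product is not reapplied until after the 6-month examination, and Protocol 2.2 describes arrest as rapid, citing 72% of cavities hard within 2 weeks. If late new arrest is rare, little relapse can hide, as the first row of the table shows. This limits the likely size. It does not remove the gap: the documents give no late-arrest rate, and the assumed 45% arrest under placebo shows that arrest without SDF is expected, at unstated times.

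The direct estimate has its own weakness. Hardness is an examiner's judgement, and Protocol Appendix A directs doubtful lesions to be scored active. Among lesions selected as arrested at 3 months, scoring error at either visit looks like relapse, so crude retention will tend to be too low. This stands as a caveat to report.

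**Conclusion.** The point holds as a limited mismatch between one secondary hypothesis and its analysis. The comparison of overall proportions bounds lesion-level retention without identifying it: 18% to 100% at the plan's 55%, 73% to 100% at the literature's 79%, given equal proportions at both visits. Practical size depends on an unknown rate of late new arrest; for assumed rates of 5% to 30%, hidden relapse is about 4% to 25% at 55% arrested and about 1% to 8% at 79%.

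It would be too strong to say that the planned model is wrong, or that it tells nothing about retention. The model fits the stated aim, and at high arrest rates the bounds are informative. Nor does the point reach the main results. Sub-Aim 2b is not one of the two key secondary endpoints in the SAP 6.11.4 hierarchy, and Protocol 3.1 and 3.2.2 exclude the secondary outcomes from labeling claims. The severity is low.

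**What to change.** Keep the marginal repeated-measures model for the effect-over-time aim, and add to Sub-Aim 2b in SAP 6.11.4:

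- By arm, the lesion transition table of 3-month against 6-month status.
- By arm, the proportion of trial lesions arrested at 3 months that are still arrested at 6 months, with a 95% CI clustered by child and adjusted for site. Early exits count as not arrested, as in SAP 6.11.1.
- A statement that the between-arm contrast in retention is descriptive, because it conditions on a status reached after randomisation.
- A missing-data rule. SAP 6.11 names multiple imputation for the 6- and 8-month analyses only. Either use the imputed data with 3-month status imputed as well, or state that the analysis uses complete pairs.
- A sentence that a non-significant difference between visits will not be read as stability.
- A note that hardness scoring error at either visit makes crude retention look somewhat lower than it is.

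The cost is a paragraph of SAP text, one table and one estimate by arm, from examinations already scheduled at 3 and 6 months. SAP section 6 allows additional analyses if justified and documented in the study report; if treatment codes are already open, this one should be labelled as added.

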6.11.5. Tertiary Efficacy Hypotheses, Endpoints, and Analyses

The P-CPQ (Sub-Aim 4a), FIS (Sub-Aim 4a), and satisfaction and acceptability scores (Sub-Aim 4b) will be compared between the SDF and placebo-treated groups using analysis of covariance (ANCOVA). The models will include study site as a covariate due to stratified randomization by site. Additional ANCOVA models will consider the effects of covariates and their interactions with the treatment effect.

Changes in the color of treated lesions over time will be summarized by group.

The family's experiences with ECC, child's brushing and dietary habits, and color change will be examined as additional covariates for the analyses of satisfaction and acceptability scores.

The total number of episodes of pain associated with trial teeth per participant (calculated by adding all reports of pain throughout the trial verified by a clinical exam to be associated with a trial tooth) during the follow-up period and the DDQ scores will be summarized for the SDF and placebo treated groups. Due to the small number of participants with any pain, no statistical comparisons will be performed for the number of episodes of pain or the DDQ scores.

Additional analyses of the proportion of arrested lesions at 3-months, 6-months, and 8-months will extend the GEE models for binary outcomes to include covariates and their interactions with the treatment effect; covariates will include race/ethnicity, gender, age, trial site, initial ICDAS score, tooth location (anterior/posterior; as there are some data in the literature to suggest a difference in SDF efficacy) and number of affected teeth. Interactions of the covariates with treatment will be explored to examine the results for differential treatment effects. However, the analyses are not specifically powered to detect these interactions. Due to the small number of participants with any pain, no analyses which include covariate effects on the binary pain outcomes will be performed.

